To allow the use of PCS in zavegeptant pediatric studies, a bridging or comparative study comparing the PCS approach with an equivalent conventional sampling technique is needed as a regulatory expectation to demonstrate the concordance of data from PCS in a controlled environment prior to implementation in large-scale clinical trials.³⁶ Therefore, the primary objective of this study is to establish the correlation between zavegeptant concentration from samples collected using PCS devices compared to conventional venous blood sampling. PK sampling time points and duration, as described in [SoA, Table 2](#), were selected to adequately capture the rapid absorption of zavegeptant, since it has a T_{max} of 0.54 hours, as well as zavegeptant elimination phase. Based on zavegeptant PK data, zavegeptant has an elimination half-life of ~ 3 hours and an effective half-life of 6.55 hours following a single zavegeptant 10 mg IN dose. For Tasso bridging analysis, having PK samples that covers zavegeptant relevant concentration up to 12 hours will be sufficient to have adequate concentration-time comparison between the 2 methods. While for the Japanese participants, having PK timepoints up to 24 hours will cover >3 half-lives, which will be sufficient to adequately estimate zavegeptant half-life in Japanese. That's why 24 hours PK samples will only be requested for Japanese enrolled participants, as described in [SoA, Table 2](#).

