A healthy participant population is considered for the study because healthy participants with no concomitant diseases and using no concomitant medications represent a homogenous population allowing for proper evaluation of the PK, safety, and tolerability of a drug without confounding factors. Six PK samples will be collected from the Tasso devices at the same time of collecting venous blood samples, as described in the [SoA, Table 2](#). Those 6 Tasso-venous paired samples collected in 7 participants for each device ($7 \times 6 = 42$ data points) are sufficient to meet the scientific community recommendation for having an adequate Tasso-venous phlebotomy PK bridging study.³⁶ Different PK sampling times were selected to cover the concentration-time profile of zavegeptant IN. Of note, blood-to-plasma ratio samples will be aliquoted from the same venous blood draw as specified in the [SoA, Table 2](#). These samples will be crucial for determining the blood-to-plasma ratio value for each participant to convert the dried blood concentrations collected using Tasso-M20 to their equivalent plasma concentrations for adequate comparison between the 2 methods.

If feasible, 4 Japanese participants will be enrolled among the 14 participants planned for this study to determine the PK and safety of zavegeptant IN in this population since there is no PK and safety data available for the use of zavegeptant IN in this population. Leveraging this data will be useful in supporting the development of zavegeptant IN in Japan. However, the recruitment of these Japanese participants will be optional, and the completion of this trial will not require their enrollment.

As noted earlier, data from clinical trials of zavegeptant IN formulation have shown dysgeusia (bad/metallic/bitter taste) as the most common treatment-emergent adverse event following zavegeptant administration (refer to IB). We hypothesize that the mechanism of dysgeusia associated with zavegeptant nasal spray administration relates to the postnasal dripping of residual spray into the oral cavity and contact with the posterior tongue and taste buds, triggering the taste receptor cells. To test this hypothesis and better understand this adverse event (its intensity, onset, and duration), a taste assessment questionnaire will be performed at 1 (immediately after dosing), 5, 10 and 20 minutes after zavegeptant IN administration.

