9.3.2.2. Statistical Methods for Pharmacokinetic Data

The plasma concentration of zavege pant will be listed and descriptively summarized by nominal sampling time, for each Tasso device by blood collection method (Tasso and venous), and by race (non-Japanese and Japanese), as data permit. Individual participant and summary profiles (mean and median plots) of the plasma concentration-time data will be plotted using actual and nominal sampling times, respectively. The correlations of paired Tasso-Plus versus venous phlebotomy concentrations and paired Tasso-M20 versus venous phlebotomy concentrations will be reported.

The PK parameters of zavege pant will be listed and summarized descriptively for each Tasso device by blood collection method (Tasso and venous), and by race (non-Japanese and Japanese), as data permits. For AUC_{last} , AUC_{inf} , and C_{\max} , box and whisker plots for individual participant parameters will be constructed for each Tasso device by blood collection method and overlaid with geometric means. The PK parameter analysis set will be used.

Additional specifications about the tables, listings, and figures will be outlined in the SAP.

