2.3. Study Design

This is a single-center, Phase 1, non-randomized, open-label, 2-period study in healthy participants to primarily evaluate the correlation of zavegepant concentration from samples collected using Tasso Devices (Tasso-Plus and Tasso-M20) compared to standard venous phlebotomy. This study consists of two periods which will include approximately 14 participants.

In period 1, 50% (n=7) of participants will use Tasso-Plus, while the other 50% (n=7) will use Tasso-M20. All 14 participants will have 6 PK samples collected using the assigned Tasso device simultaneously with collecting venous blood samples at the following time points, 30 minutes, 1, 2-, 4-, 8-, and 12-hour postdose, as described in the SoA, Table 2 (in the protocol). In addition, taste assessments will be performed at time intervals of 1 (immediately after dosing), 5, 10 and 20 minutes after zavegepant IN administration. Also, if feasible, 4 Japanese participants will be enrolled among those 14 participants to evaluate the PK and safety of zavegepant IN in Japanese vs. non-Japanese participants. For Japanese participants, a total of 12 venous blood samples will be collected at the following time points, 0, 15 minutes, 30 minutes, 1, 1.5-, 2-, 3-, 4-, 6-, 8-, 12-, and 24-hour (refer to SoA, Table 2 in the protocol).

In period 2, a butterscotch candy will be given 5 minutes before administering the zavegepant IN study intervention. Taste assessment will also be performed after zavegepant IN administration with a butterscotch candy in period 2. For taste assessment, each participant will record the sensory attributes at timed intervals of 1 (immediately after dosing), 5, 10 and 20 minutes after zavegepant administration in each period.

Healthy participants will be screened within 28 days prior to the first administration of the study intervention to confirm that they meet the participant selection criteria for the study. Eligible participants will be admitted to the CRU on Day -1 and will be confined in the CRU until Discharge on Day 3 (SoA in the protocol), approximately 24 hours after the second dose. Enrolled participants will receive a single IN dose of zavegepant 10 mg (0.1 mL) in each period. PK venous blood samples as well as Tasso PK sampling, using Tasso-Plus and

Tasso-M20, will be collected at specified intervals as per SoA (Table 2) in the protocol for PK assessments.

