3.1.2. Zavegepant PK Parameters

Zavegepant PK parameters from samples collected using Tasso and venous phlebotomy will be derived from the concentration-time profile using non-compartmental methods, as detailed in Table 2. Actual PK sampling times will be used in the derivation of PK parameters. In the case that actual PK sampling times are not available, nominal PK sampling time will be used in the derivation of PK parameters.

Table 2. Definitions of PK Parameters

Parameter	Definition	Method of Determination
C_{max}	Maximum plasma concentration	Observed directly from data
AUC_{last}	Area under the plasma concentration-time profile from time 0 to the time of the last quantifiable concentration (C_{last})	Linear/Log trapezoidal method
AUC_{inf}^a	Area under the plasma concentration-time profile from time 0 extrapolated to infinite time	$AUC_{last} + (C_{last}/k_{el})$, where C_{last} is the predicted plasma concentration at the last quantifiable time point estimated from the log-linear regression analysis
T_{max}	Time for C_{max}	Observed directly from data as time of first occurrence
$t_{1/2}^a$	Terminal half-life	$\log_2(2)/k_{el}$, where k_{el} is the terminal phase rate constant calculated by a linear regression of the log-linear concentration-time curve
CL/F^a	Apparent clearance	Dose/ AUC_{inf}
V_z/F^a	Apparent volume of distribution	Dose/($AUC_{inf} \times k_{el}$)

a. If data permits.

PK parameters from samples collected using Tasso-M20 will be adjusted for B/P ratio.

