6. ANALYSES AND SUMMARIES

6.1. Primary Endpoints

6.1.1. Zavegepan PK Concentrations

The plasma concentrations and plasma equivalent concentrations (derived from Tasso-M20 samples) of zavegepan will be listed and descriptively summarized by nominal PK sampling time, for each collection method (Tasso-Plus, Tasso-M20 and venous phlebotomy), and by race (non-Japanese and Japanese), as data permit for the PK Concentration Analysis Set. Individual participant and summary profiles (mean and median plots) of the plasma concentration-time data will be plotted by collection method and race using actual and nominal times, respectively. Mean and median zavegepan plasma concentration profiles will be presented on both linear and semi-log scales.

Presentations for zavegepan plasma concentrations will include:

- A listing of all concentrations sorted by participant ID, collection method, race and nominal time postdose. The concentration listing will also include the actual times. Deviations from the nominal time will be provided in a separate listing.
- A summary of concentrations by collection method and by race, and nominal time postdose, where the set of statistics will include n, mean, median, SD, %CV, minimum, maximum and the number of concentrations above the LLQ.
- Median concentrations time plots (on both linear and semi-log scales) against nominal time postdose by collection method and by race (all collection methods on the same plot per scale (similarly for race), based on the summary of concentrations by collection method, race and time postdose).
- Mean concentrations time plots (on both linear and semi-log scales) against nominal time postdose by collection method and race (all collection methods on the same plot per scale (similarly for race), based on the summary of concentrations by collection method, race and time postdose).
- Individual concentration time plots by collection method and by race (on both linear and semi-log scales) against actual time postdose (there will be separate spaghetti plots for each collection method and race per scale).
- Individual concentration time plots by participant (on both linear and semi-log scales) against actual time postdose [there will be separate plots for each participant (containing all collection methods and all race) per scale].

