The correlations of paired Tasso-Plus versus venous phlebotomy concentrations and paired Tasso-M20 versus venous phlebotomy concentrations will be reported. Furthermore, Bland-Altman plot analysis will be performed for each pair to evaluate the bias and SD of the bias between the mean differences and to estimate an agreement interval within a 95% confidence limit.

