6.1.2. Zavegepant PK Parameters

The PK parameters of zavegepant will be listed and summarized descriptively for each collection method (Tasso-Plus, Tasso-M20 and venous phlebotomy), and by race (non-Japanese and Japanese), as data permits for the PK Parameter Analysis Set. Each zavegepant PK parameter will be summarized including the set of summary statistics as specified in Table 3.

For AUC_{last} , AUC_{inf} , and C_{max} , box and whisker plots for individual participant parameters will be constructed for each collection method and overlaid with geometric means.

Table 3. PK Parameters to be Summarized Descriptively by Collection Method and Race

Parameter	Summary Statistics
AUC_{inf} , AUC_{last} , C_{max} , CL/F , V_z/F	N, arithmetic mean, median, SD, %CV, minimum, maximum, geometric mean and geometric %CV
T_{max} , T_{last}	N, median, minimum, maximum
$t_{1/2}$	N, arithmetic mean, median, SD, %CV, minimum, maximum

Supporting data from the estimation of $t_{1/2}$ and AUC_{inf} will be listed by collection method and by race: terminal phase rate constant (k_{el}); goodness of fit statistic from the log-linear regression (r^2); the percent of AUC_{inf} based on extrapolation ($AUC_{extrap}\%$); and the first, last, and number of time points used in the estimation of k_{el} . This data may be included in the clinical study report.

For the Tasso vs. Venous comparison, natural log-transformed zavegepant AUC_{inf} (if data permit), AUC_{last} and C_{max} will be analyzed using a mixed effect model with blood collection method as fixed effect and participant as random effect. Estimates of the adjusted mean differences (Test – Reference) and corresponding 90% CIs will be obtained from the model with Venous as the Reference group and Tasso-M20 (or Tasso-Plus) as the Test group. The adjusted mean differences and 90% CIs for the differences will be exponentiated to estimate the adjusted geometric means ratio (Test/Reference) and 90% CIs for the ratios.

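### If Japanese participants enrol, the Tasso/venous AUClast ratio compares a 12 h Tasso profile with a 24 h venous profile in the same person

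*SAP*

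**What the plan says.** **Sampling.** Protocol 4.1 and Table 2 give all participants Tasso samples at 0.5, 1, 2, 4, 8 and 12 h, each paired with a venous sample. SAP 2.3 adds: "For Japanese participants, a total of 12 venous blood samples will be collected at the following time points". The extra venous times are 0, 0.25, 1.5, 3, 6 and 24 h. Up to 4 of the 14 may be Japanese, and Protocol 4.2 says "the recruitment of these Japanese participants will be optional".

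**Parameters.** SAP 3.1.2 derives the parameters by non-compartmental methods from each method's profile. AUClast runs "from time 0 to the time of the last quantifiable concentration", and Cmax is the highest observed value.

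**Model.** In SAP 6.1.2 the responses are the logs of Cmax, of AUClast and, where it can be derived, of AUCinf. The SAP says that they "will be analyzed using a mixed effect model with blood collection method as fixed effect and participant as random effect", with venous as Reference and a Tasso device as Test. The output is a geometric mean ratio (GMR) with a 90% CI. There is no race term and no rule on shared times.

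**Paired concentrations.** In SAP 6.1.1, besides correlations, "Bland-Altman plot analysis will be performed for each pair".

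**Displays.** Under Protocol 9.3.2.2, PK parameters are "listed and summarized descriptively for each Tasso device by blood collection method (Tasso and venous"). SAP 6.1.1 summarises "for each collection method (Tasso-Plus, Tasso-M20 and venous phlebotomy), and by race (non-Japanese and Japanese"), and SAP 6.1.2 uses the same three groups. SAP 2.1 declares no modifications to the protocol's analysis.

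**The concern.** In a Japanese participant the Reference AUClast can include area from 12 to 24 h that the Test AUClast cannot contain. The venous Cmax is also the maximum of more samples than the Tasso Cmax. Both differences push the Tasso/venous ratio down, and both occur inside one person, so a participant effect does not absorb them.

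PK parameters by sampling method are a primary endpoint. Readers will take these ratios and intervals as the size of the device difference, and a schedule artefact could pass for under-recovery by the device. Protocol 4.2 itself treats data to 12 h as enough for the bridging comparison and keeps the 24 h sample for estimating half-life in Japanese participants. The SAP model does not carry that separation forward.

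A smaller point is the displays. The three-group layout sets 7 Tasso participants beside up to 14 venous participants, half of whom used the other device.

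**Working it through.** **The plan's own figure.** 7 participants × 6 pairs = 42 pairs per device (Protocol 9.5). This reproduces, and those paired data are not affected.

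**Inputs from the documents.** The two schedules above; Tmax 0.54 h; "an elimination half-life of ~ 3 hours and an effective half-life of 6.55 hours" (Protocol 4.2).

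**Assumptions.**
- One-compartment curve with first-order input, C(0) = 0, and no true device difference.
- The lower limit of quantification is not given, so the 24 h sample is taken both as quantifiable and as not.
- The 6.55 h effective half-life serves only as an upper bound on the late decline.

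**Curve.** C(t) ∝ ka/(ka − k) × [exp(−kt) − exp(−ka·t)], with k = ln 2 / half-life and ka solved from ln(ka/k)/(ka − k) = 0.54. This gives ka = 6.37/h (3 h) and 8.15/h (6.55 h). Areas use the linear-up/log-down trapezoid, in relative units.

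**One Japanese participant, Tasso AUClast / venous AUClast.**

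| Half-life | 24 h quantifiable | 24 h below quantification |
|---|---|---|
| 3 h | 3.9289/4.2744 = 0.919 | 3.9289/4.0112 = 0.979 |
| 6.55 h | 6.6231/8.6526 = 0.765 | 6.6231/6.7188 = 0.986 |

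Moving Tmax from 0.25 to 1.0 h gives 0.93–0.91 (3 h) and 0.76–0.77 (6.55 h) with the 24 h sample quantifiable, and 0.97–0.99 without it.

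**Device group of 7 with m Japanese.** GMR = ratio^(m/7). For example, 0.919^(2/7) = 0.976 and 0.765^(2/7) = 0.926.

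| m of 7 | 3 h, 24 h quantifiable | 6.55 h, 24 h quantifiable | 24 h below quantification (3 h; 6.55 h) |
|---|---|---|---|
| 0 | 1.000 | 1.000 | 1.000; 1.000 |
| 1 | 0.988 | 0.963 | 0.997; 0.998 |
| 2 | 0.976 | 0.926 | 0.994; 0.996 |
| 3 | 0.965 | 0.892 | 0.991; 0.994 |
| 4 | 0.953 | 0.858 | 0.988; 0.992 |

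**How many Japanese participants per device.** The split is not specified. If 4 enrol and fall to devices by chance (an assumption), P(m) = C(4,m)·C(10,7−m)/C(14,7). For m = 0 this is 120/3432 = 0.035, so a given device has at least one with probability about 0.97. The commonest split, 2 and 2, has probability 1512/3432 = 0.44.

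**Interval.** 20,000 simulated groups of 7, independent lognormal error on every sample, paired t interval on 6 df, 24 h sample quantifiable. Coverage is of the true ratio 1 by the nominal 90% CI.

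| m of 7 | Half-life | Coverage, 10% error | Coverage, 20% error |
|---|---|---|---|
| 2 | 3 h | 0.84 | 0.87 |
| 2 | 6.55 h | 0.83 | 0.82 |
| 4 | 3 h | 0.55 | 0.77 |
| 4 | 6.55 h | 0.10 | 0.36 |

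With m = 2, the log half-width goes from 0.045 to 0.052 (3 h) or 0.105 (6.55 h) at 10% error, and from 0.089 to 0.090 or 0.129 at 20%. With venous parameters from the six shared times, the GMR is 1.00 and coverage 90% in every setting.

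**Cmax.** At 10–20% error the ratio in one Japanese participant is 0.954–0.993. The device GMR is 0.987–0.998 (2 of 7) and 0.974–0.996 (4 of 7). At 30% error with between-participant variation in ka (log-SD 0.5), the lowest values are 0.975 and 0.951.

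**Displays.** With no device effect, the geometric mean of 7 participants relative to that of all 14 has a 90% range of exp(±1.645 × SDlog × √(1/7 − 1/14)). For assumed between-participant CVs of 30%, 50% and 70% this is 0.88–1.14, 0.81–1.23 and 0.76–1.32. The range describes the side-by-side display, not the model ratios.

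**The case against.** **The effect is doubly conditional.** Japanese enrolment is optional, and a material effect also needs a quantifiable 24 h sample. On the 3 h curve the 24 h concentration is about 0.46% of Cmax, so it may well fall below quantification. The GMR then stays at about 0.99 or above, with coverage of 86–90%. This stands and keeps the severity down.

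**The large figures lean on 6.55 h.** Protocol 2.2.2.3 gives a terminal half-life of about 3 h and describes the effective half-life as reflecting the whole profile, so 6.55 h is not a terminal slope. That is fair, and the 3 h figures are the better supported. But Protocol 4.2 describes 24 h as more than three half-lives. That sits closer to 6.55 h (24/6.55 = 3.7) than to 3 h (24/3 = 8), so 6.55 h remains usable as a bound.

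**Other outputs would reveal the mismatch.** AUCinf is in the same model and depends less on the sampling horizon. Tlast is summarised and the extrapolated percentage is listed. These help a careful reader but do not correct the AUClast ratio or its interval.

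**The main bridging evidence is intact.** Correlations and Bland-Altman analyses use simultaneous pairs, and there is no hypothesis or decision rule. This stands.

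**The coverage figures describe one reading.** SAP 6.1.2 does not say whether one three-level model or two device-specific models are fitted. The simulation uses the device-specific reading. The bias does not depend on that choice, since it lies within the participant.

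**The SAP may modify the protocol.** Protocol section 9 allows this, and the SAP's version history discloses the display change and the added ratios. Section 2.1 is still inaccurate, but that is a wording matter.

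**Conclusion.** The concern holds. As written, the AUClast comparison can return a ratio below 1 for a device identical to venous sampling, always in the same direction, whenever Japanese participants are in that device group. The best-supported size (3 h half-life, 24 h sample quantifiable) is a 2% loss with 2 of 7 Japanese and 5% with 4 of 7. The upper bounds at 6.55 h are 7% and 14%. Clear widening of the interval appears mainly at the upper bound; at 3 h and 20% error it is negligible. The Cmax effect is small. All sizes rest on the assumed curve, the error levels, the device split and an unstated quantification limit; the mismatch itself rests only on the documents.

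This is a should-fix. The pooled venous displays and the entry in SAP 2.1 are minor, separate points that hardly touch the model ratios.

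**What to change.** 1. In SAP 6.1.2, for the device comparison only, derive venous AUC and Cmax from the six shared nominal times. Compare AUC over one named common interval: either 0–12 h, or up to the last time at which both methods are quantifiable in that participant. Keep the full 24 h venous profile for describing Japanese PK.
2. State that the mixed model is fitted separately per device on that device's own participants, and show venous results within each device group as in Protocol 9.3.2.2.
3. In SAP 2.1, list the display change and the added GMR models.

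**Cost.** Some SAP wording and one extra set of non-compartmental parameters; no new samples. Fitting per device costs some degrees of freedom (t = 1.94 on 6 df against about 1.78 on 12 df). Shared times did not widen the AUClast interval when the 24 h sample was quantifiable: with 2 of 7 Japanese and 10% error, the log half-width was 0.045 matched against 0.052–0.105 unmatched.

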9.5. Sample Size Determination

Approximately 14 evaluable participants will be enrolled (7 for Tasso-Plus and 7 for Tasso-M20). There is no statistical hypothesis for this study. The sample size determination for this study was based on the established scientific recommendation for having 30 to 40 PK data points to ensure adequate comparison between PCS (test) and venous sampling.³⁶ With a sample size of 7 evaluable participants per each Tasso device, and 6 Tasso-venous paired PK samples collected, there will be sufficient PK data points ($7 \times 6 = 42$ data points from each Tasso device) to meet the scientific community recommendation for having an adequate Tasso-venous phlebotomy PK bridging study.

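### SAP PK displays set each Tasso device (n=7) against venous data pooled over both device groups (n=14), and the ratio model is not stated to be per device

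*SAP*

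**What the plan says.** **Design.** SAP 2.3: "50% (n=7) of participants will use Tasso-Plus, while the other 50% (n=7) will use Tasso-M20". It adds: "All 14 participants will have 6 PK samples collected using the assigned Tasso device simultaneously with collecting venous blood samples". The venous and Tasso samples of one device group therefore come from the same 7 people, and nobody uses both devices.

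**Protocol layout.** Under Protocol 9.3.2.2 the PK parameters are "listed and summarized descriptively for each Tasso device by blood collection method (Tasso and venous"). Concentrations and box plots follow the same device-by-method pattern, and the synopsis describes the box plots in the same way.

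**SAP layout.** SAP 6.1.1 summarises concentrations "for each collection method (Tasso-Plus, Tasso-M20 and venous phlebotomy"), and its mean and median plots put "all collection methods on the same plot per scale". Under SAP 6.1.2 the PK parameters are "listed and summarized descriptively for each collection method (Tasso-Plus, Tasso-M20 and venous phlebotomy"), with box plots by collection method. Venous is thus one group containing all 14 participants. The version history records the move to presentation by collection method, but SAP 2.1 declares no modifications to the protocol's plan.

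**Model.** SAP 6.1.2 analyses log AUCinf, AUClast and Cmax with collection method as a fixed effect and participant as a random effect. Ratios and 90% CIs are taken "with Venous as the Reference group and Tasso-M20 (or Tasso-Plus) as the Test group". It does not say whether method has three levels in one fit or two levels in each of two fits, which venous records enter, or whether the residual variance may differ by device.

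**Paired analyses kept.** SAP 6.1.1 reports correlation and Bland-Altman separately for Tasso-Plus with venous and for M20 with venous. It also plots each participant's profiles with all methods together.

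**The concern.** In the SAP displays, half of the venous group never used the device being compared with it. If the 7 Tasso-Plus users happen to have higher exposure than the 7 M20 users, Tasso-Plus will sit above pooled venous and M20 below it even when both devices are perfect. The study is described as non-randomized, and SAP 6.1 plans no balancing of the device groups on race or exposure, so such a difference need not be only chance.

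Pooling also mixes schedules. Japanese participants, if enrolled, have 12 venous times against 6 Tasso times (Protocol Table 2). The venous group then includes times, up to 24 hours, that no Tasso sample can match.

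The model raises a separate question. If it is one fit with a single residual variance, both devices receive the same standard error. Equal error is not obvious. Under Protocol 8.5, M20 takes about 100 µL of dried blood, while Tasso-Plus takes 300-500 µL of liquid blood to give serum. Under SAP 3.1.1, only M20 values are divided by an individual blood-to-plasma ratio. If one ratio is used per participant, its error is shared by all six of that person's M20 values and does not average out in AUC.

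At stake is how the device-specific summaries, plots and ratio intervals for AUC and Cmax are read.

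**Working it through.** **Inputs from the documents.** Protocol 9.5 gives "7 evaluable participants per each Tasso device, and 6 Tasso-venous paired PK samples collected". This reproduces: 7 × 6 = 42 pairs per device, and 7 + 7 = 14 participants. The confidence level is 90% (SAP 6.1.2).

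**Assumptions.** The documents give no CVs or error SDs. I take between-person CV 30%, 50% and 70%, within-person CV 10% (20% as a check), and a ratio of device error SDs from 1 to 3. On the log scale, σ² = ln(1 + CV²).

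**1. Displays, no true device bias**

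The device mean minus the pooled venous mean contains half the difference between two independent means of 7. Its between-person variance is (1/4)(2/7)σb² = σb²/14. Within-person error adds σw²/7 + σw²/14 = 3σw²/14. Beside the device's own venous data, σb² cancels and the variance is 2σw²/7.

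Worked case, CV 50% and 10%:
- σb² = ln 1.25 = 0.2231 and σw² = ln 1.01 = 0.00995.
- Pooled variance = 0.01594 + 0.00213 = 0.01807, so SE = 0.134 and the 95% limits are exp(±1.96 × 0.134) = 0.77-1.30.
- Own-venous variance = 2 × 0.00995/7 = 0.00284, so SE = 0.053 and the limits are 0.90-1.11.

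| Between-person CV | Within-person CV | Device vs pooled venous | Device vs own venous |
|---|---|---|---|
| 30% | 10% | 0.84-1.20 | 0.90-1.11 |
| 50% | 10% | 0.77-1.30 | 0.90-1.11 |
| 70% | 10% | 0.71-1.41 | 0.90-1.11 |
| 30% | 20% | 0.79-1.27 | 0.81-1.23 |
| 50% | 20% | 0.74-1.36 | 0.81-1.23 |
| 70% | 20% | 0.69-1.46 | 0.81-1.23 |

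**2. Ratio intervals**

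*Separate fit per device.* This is the paired analysis on 7 differences, with half-width t(0.95, 6) × s/√7 and t = 1.943. Simulated coverage is 0.90 for both devices at every SD ratio tried.

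*Joint fit with one residual variance.* Treating the variance of the paired differences as pooled, the half-width is t(0.95, 12) × √[(s₁² + s₂²)/2]/√7 with t = 1.782. Simulated coverage, 300,000 trials per row:

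| Ratio of SDs of paired differences | More precise device | Less precise device |
|---|---|---|
| 1 | 0.90 | 0.90 |
| 1.25 | 0.93 | 0.87 |
| 1.5 | 0.96 | 0.84 |
| 2 | 0.98 | 0.81 |
| 3 | 0.996 | 0.78 |

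Example at ratio 2, with SDs of 0.10 and 0.20: the pooled SD is √[(0.01 + 0.04)/2] = 0.158, so both devices get 1.782 × 0.158/2.646 = 0.106. Separately they get 1.943 × 0.10/2.646 = 0.073 and 1.943 × 0.20/2.646 = 0.147.

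*Full three-level REML fit* (2,000 trials per setting). With equal error CVs of 15%, coverage is 0.89-0.91 and intervals are about 6-10% narrower than separate ones. With error CV 10% for venous and one device and 20% for the other, the SD ratio of the differences is √[(0.00995 + 0.03922)/(2 × 0.00995)] = 1.57, and coverage is 0.95-0.97 and 0.82-0.83. Across all settings, between-participant information gets about 2-14% of the weight in estimating the difference between devices, so the estimates stay close to the paired ones.

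**The case against.** The strongest reply is that the inferential core is already paired. Correlation and Bland-Altman are run per device, the participant random effect links each Tasso value to that person's venous value, and individual plots overlay the methods. A reader of the three-group displays might infer that the SAP has abandoned pairing. It has not.

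A reader might also infer that the 90% CIs are wrong for both devices. The documents do not support that. Naming M20 with Tasso-Plus as the alternative test group fits two separate two-group models at least as well as one joint model, and then there is no CI error. Even a joint fit is valid if the device errors are equal, and the documents give no error figures.

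On the displays, Protocol 9.3.1 speaks of summaries by blood collection method, Protocol section 9 lets the SAP modify the plan, and the version history discloses the change. The displays are descriptive and no hypothesis is tested. Even the own-venous display ranges over 0.81-1.23 at within-person CV 20%.

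All of this stands as a limit on the point, but some of it remains open. Protocol 9.3.2.2 is the specific text for PK and its layout is unambiguous, so SAP 2.1 is inaccurate. Bland-Altman addresses concentrations and does not repair the AUC and Cmax summaries or box plots. The SAP leaves the form of the model for a primary endpoint to the programmer.

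**Conclusion.** The display defect is established from the text: the SAP drops the protocol's device-by-method layout without declaring it. Its size depends on assumed CVs. At within-person CV 10%, the 95% range of a purely spurious ratio runs from 0.84-1.20 to 0.71-1.41, against 0.90-1.11 with the protocol's layout. These ranges treat device allocation as unrelated to exposure.

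The interval problem is conditional. It needs a joint fit, one residual variance and unequal device errors. The blood-to-plasma conversion of M20 alone makes unequal errors plausible, but their size is unknown. At assumed SD ratios of 1.5 and 2, coverage is 0.96/0.84 and 0.98/0.81 (more precise/less precise device) against a nominal 0.90. What the documents do establish is that the model is under-specified.

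It would also go too far to call these intervals the main evidence for choosing a device. No section describes such a choice or ties a decision to them, and the stated primary purpose is concentration correlation, which is analysed per device. The point deserves correction before analysis but does not undermine the study.

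**What to change.** 1. In SAP 6.1.1 and 6.1.2, restore the Protocol 9.3.2.2 layout: for each device, show Tasso and venous from the same participants at the six shared times (0.5, 1, 2, 4, 8 and 12 hours). For the device comparison, derive venous parameters from those times too. Keep the full 12-sample venous profile for the Japanese evaluation.
2. In SAP 6.1.2, state that the log-parameter model is fitted separately per device on its own participants, or jointly with a residual variance for each device.
3. In SAP 2.1, list whatever departures from the protocol remain.

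The cost is SAP wording and a by-device split in the programs; no new data are needed. Separate fits have 6 rather than 12 residual degrees of freedom, so intervals are about 9% wider if the variances are in fact equal (1.943/1.782 = 1.09).
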